Appendix B: Case Report Form

The case report forms for the study are kept under a separate cover and are available upon request.

1.0 SYNOPSIS OF STUDY DESIGN

1.1 Purpose of the Statistical Analysis Plan

This statistical analysis plan (SAP) is intended to provide a detailed and comprehensive description of the planned methodology and analysis to be used for Clinical Study Protocol for the Evaluation of ICD Defibrillation Systems in a 1.5T Magnetic Resonance Imaging (MRI) Environment in China, the CRD-930 (ABT-CIP-10238) clinical investigation. This plan is based on the ABT-CIP-10238 Ver. D, 30SEP2019 Clinical Investigation Plan (CIP).

1.2 Clinical Investigation Objectives

The objective of this clinical study is to evaluate the safety and effectiveness of the Ellipse VR/DR implantable cardiac defibrillators (ICDs) and the Quadra Assura MP cardiac resynchronization therapy defibrillators (CRT-Ds), with Durata or Optisure defibrillation leads, Tendril STS or Isoflex pacing leads, and the Quartet quadripolar leads in a 1.5T MRI environment for MR-conditional labeling expansion of these market-approved ICD/CRT-D systems in China.

1.3 Clinical Investigation Design

This is a prospective, multi-center, single-arm study to evaluate the safety and effectiveness of the Ellipse VR/DR ICDs, and the Quadra Assura MP CRT-D, with Durata or Optisure defibrillation leads, Tendril STS or Isoflex pacing leads, and the Quartet quadripolar LV lead in a 1.5T MRI environment for MR-conditional labeling expansion in China.

This study will be conducted in at least 6 centers in China and at least 60 subjects who provide consent for participation will be enrolled. Subjects will be considered enrolled after providing consent. Subjects will be implanted with any one of the device/lead combination groups outlined as following, depending on their clinical need as determined by the Investigators. At least 15 subjects will be enrolled in each group.

- **Group 1** will have at least 15 enrolled subjects with the Ellipse VR single-chamber ICD with a Durata lead in the right ventricle (RV).
- **Group 2** will have at least 15 enrolled subjects with the Ellipse DR dual-chamber ICD with a Durata lead in the RV and a Tendril STS lead in the right atrium (RA).
- **Group 3** will have at least 15 enrolled subjects with the Ellipse DR dual-chamber ICD with a Optisure lead in the RV and a Isoflex lead in the RA.
- **Group 4** will have at least 15 enrolled subjects with a Quadra Assura MP CRT-D and an Optisure or Durata lead in the RV, an Isoflex or Tendril STS lead in the RA, and a Quartet lead in the left ventricle (LV).

A prospective, multi-center, non-randomized, open-label, single arm clinical study design was chosen to generalize the study results [REDACTED]

[REDACTED]. This study intends to provide clinical data from a local Chinese population to supplement IDE clinical data from a population in the United States and Europe for submission to the

Statistical Analysis Plan

NMPA in support of a marketing application of MRI labeling expansion for these ICD/CRT-D systems in China.

1.4 Endpoints

1.4.1 Primary Safety Endpoint

Freedom from MRI-scan related complications related to the ICD/CRT-D device and/or leads from the time of the MRI scan to 1-month post-MRI scan testing.

1.4.2 Primary Effectiveness Endpoints

- #1: Proportion of leads with a capture threshold increase of $\leq 0.5V$ at 0.5ms for RA and RV leads and $\leq 1.0V$ at 0.5ms for LV leads from pre-MRI scan to 1-month post-MRI scan testing.
- #2: Proportion of leads with a sensing amplitude decrease of $\leq 50\%$ from pre-MRI scan to 1-month post-MRI scan testing.

1.4.3 Descriptive Endpoints

Descriptive endpoints are reported using only summary statistics and no hypothesis tests will be performed.

The following data will be collected:

1. Demographics: gender, age, ethnicity, race, cardiac disease history, arrhythmia history, indication for ICD/CRT-D implant, history of smoking, etc.
2. Device electrical measurements at the MRI Scan Visit (pre- and post-scan) and at the 1-Month Post Scan Visit
3. ADE, SADE, USADE
4. Mortality
5. Number of non-study MRI scans
6. Summarize number of subjects that returned to usual programming after the MRI scan and number of subjects, if any, experiencing delays in reprogramming

1.5 Randomization

Not applicable.

1.6 Blinding

Not applicable.

Statistical Analysis Plan

2.0 ANALYSIS CONSIDERATIONS

2.1 Analysis Populations

[REDACTED]

[REDACTED]

[REDACTED]

[REDACTED]

2.2 Statistical Methods

This study is an observational study to meet the requirements for device approval by the NMPA. There is no endpoint hypotheses testing planned in this study. The endpoints, demographics, safety and device data will be summarized using descriptive statistics.

2.2.1 Descriptive Statistics for Continuous Variables

For continuous variables (e.g., age), results will be summarized with the numbers of observations, means, and standard deviations, with minimums and maximums. Two-sided 95% confidence intervals for the means may be presented, or otherwise will be specified.

2.2.2 Descriptive Statistics for Categorical Variables

For categorical variables (e.g. gender, cardiac disease history), results will be summarized with subject (or device/lead) counts and percentages/rates. Two-sided exact 95% Clopper-Pearson confidence intervals may be presented, or otherwise will be specified.

2.3 Endpoint Analysis

2.3.1 Primary Safety Endpoint

The primary safety endpoint is freedom from MRI-scan related complications related to the ICD/CRT-D device and/or leads from the time of the MRI scan to 1-month post-MRI scan testing. The CEC adjudicated data will be used for the primary safety endpoint analysis.

[REDACTED]

[REDACTED]

Statistical Analysis Plan

2.3.2 Primary Effectiveness Endpoints

Effectiveness endpoint #1:

Effectiveness endpoint #1 is the proportion of leads with a capture threshold increase of $\leq 0.5V$ at 0.5ms for RA and RV leads and $\leq 1.0V$ at 0.5ms for LV leads from pre-MRI scan to 1-month post-MRI scan testing.

[REDACTED]

[REDACTED]

[REDACTED]

[REDACTED]

[REDACTED]

[REDACTED]

[REDACTED]

[REDACTED]

Effectiveness endpoint #2:

Effectiveness endpoint #2 is the proportion of leads with a sensing amplitude decrease of $\leq 50\%$ from pre-MRI scan testing to 1-month post-MRI scan.

[REDACTED]

[REDACTED]

[REDACTED]

[REDACTED]

Statistical Analysis Plan

2.4 Sample Size Calculations

There is no hypothesis testing is planned in this study, and no sample size calculation or power analysis has been performed.

2.5 Interim Analysis

No formal interim analyses are planned for this study. As such, no formal statistical rule for early termination of the trial is defined. Interim study reports with descriptive analysis may be produced for regulatory or reimbursement purposes as needed.

2.6 Timing of Analysis

Analysis will be performed after all subjects in each device Group complete their 1-month post-MRI scan visit or pass their 1-month post-MRI scan follow-up visit window, and when data are available for the analysis for the respective device Group(s).

2.7 Study/Trial Success

There is no hypothesis testing planned in this study, therefore no statistical criteria are specified for success. Data will be summarized and presented descriptively.

2.8 Subgroups for Analysis

No subgroup analysis is planned.

2.9 Handling of Missing Data

A subject may discontinue from the study prior to the 1-month visit. If this situation occurs, reasons for missing primary endpoint data will be summarized to assess the plausibility if the missing data could affect subject's endpoint results.

Statistical Analysis Plan

2.10 Poolability Analysis

No poolability analysis is planned for the study.

2.11 Multiplicity Issues

Not applicable.

2.12 Adjustments for Covariates

Unless otherwise specified, no adjustments for covariates will be made for any of the variables in the analyses.

2.13 Exploratory Analysis

No exploratory analysis is planned.

3.0 DESCRIPTIVE ENDPOINTS AND ADDITIONAL DATA

The following data will be summarized descriptively as outlined in Section 2.2 Statistical Methods in the SAP, based on Analysis Cohort, or otherwise as specified.

3.1 Baseline and Demographic Characteristics

The baseline and demographic variables such as gender, age, ethnicity, race, key cardiovascular history, prior cardiac interventions, arrhythmia history, primary indication for ICD/CRT-D implant, and history of smoking, will be summarized descriptively.

3.2 Adverse Events

CEC adjudicated ADE, SADE, USADE data will be summarized in terms of the number of events, the number of subjects with event(s), and the percentage of subjects with event(s). Subjects who die or withdraw before 1-month post-MRI scan will be included in the denominator, and their last known status of event will be included in the numerator.

3.3 Subject Early Termination

Subject early termination reasons such as deaths, withdrawals, lost-to-follow-up. will be summarized at scheduled visits.

3.4 Protocol Deviation

Protocol deviations will be summarized descriptively by category.

[REDACTED]

[REDACTED]

Statistical Analysis Plan

3.5 Descriptive Endpoints or Additional Data

Following Descriptive Endpoints will be reported using only summary statistics and no hypothesis tests will be performed.

- 1) Demographics: gender, age, ethnicity, race, cardiac disease history, arrhythmia history, indication for ICD/CRT-D implant, history of smoking, etc. Refer to Section 3.1 for the detail.
- 2) Device electrical measurements: device electrical measurements at the MRI Scan Visit (pre- and post-scan) and at the 1-Month Post Scan Visit will be summarized based on Analysis Cohort subjects who undergo the 1-month post-MRI scan testing, and with evaluable device data available for analysis to be performed.
- 3) ADE, SADE, USADE: Refer to Section 3.2 for the detail.
- 4) Mortality: The number of subjects who die and the primary cause of death will be presented based on the CEC adjudicated data.
- 5) Non-study MRI scan data: The number, type, available adverse event(s), and key electrical measurements will be summarized for non-study MRI scans performed.
- 6) Summarize number of subjects that returned to usual programming after the MRI scan and number of subjects, if any, experiencing delays in reprogramming: Data will be summarized descriptively based on available information from MRI Scan form. A subject with 'Yes' to question of 'Were the MRI settings disabled after MRI scan' in MRI Scan form is considered as 'returned to usual programming after the MRI scan'.

In addition, the adverse events and mortality that are reported prior to the completion of the study pre-MRI scan visit on the All Consented subjects will be summarized separately using descriptive statistics. Listings of the adverse events and mortality with an event description will be provided as appropriate.

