8.2.1. Description of the effectiveness endpoints

- Proportion of leads with a capture threshold increase of $\leq 0.5V$ at 0.5ms for RA and RV leads and $\leq 1.0V$ at 0.5ms for LV leads from pre-MRI scan to 1-month post-MRI scan testing.
- Proportion leads with a sensing amplitude decrease of $\leq 50\%$ from pre-MRI scan testing to 1-month post-MRI scan.

8.2.2. Selection of method and time for evaluation, recording and analysis of the effectiveness endpoints

Since the objective is to evaluate the effect of MRI exposure for the ICD/ CRT-D device groups included in this study, the effectiveness parameters were selected to compare abnormal changes in device performance from pre- to 1-month post- MRI scan. The pre-MRI measurements are collected within the same day prior to the MRI scan. The 1-month post-MRI scan measurements are collected at 30 days post-MRI scan (within +14 days) to ensure any effect of the MRI exposure is captured.

The effectiveness parameters are recorded directly from the device. The device measurements will be obtained using the Merlin programmer to interrogate the device during study visits. The analysis of the effectiveness parameters will be conducted on all subjects with complete data from pre- to 1-month post-MRI scan.

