Baseline/ MRI Scan Visit	
45 (+7) days after implantation or after most recent lead revision
 
MRI scan should occur within 14 days of Baseline visit.
 
The pre-MRI scan, MRI, and post MRI scan procedures should occur on the same day.
	
Pre-MRI Scan testing
 
 Assess inclusion/exclusion criteria Screen, clear and prep subject for MRI scan Complete MRI screening form Complete MRI Hazard Checklist Administer pregnancy test – can be done up to 7 days before MRI scan Interrogate device Perform capacitor maintenance Obtain in-clinic lead measurements: bipolar capture, sense, pacing and HVLI impedances^{1,2} Setup and activate MRI Settings 
During MRI Scan
 
 Monitor subject with ECG, or pulse oximetry, and verbal communication 
Post-MRI scan testing
 
 Interrogate device Deactivate MRI Settings Obtain in-clinic lead measurements: bipolar capture, sense, pacing and HVLI impedances^{1,2} Evaluate subject for any adverse events (serious and non-serious) and submit an AE CRF (as applicable). Report deviations, screening failure/withdrawal and out of service as applicable Submit MRI scan results, e.g. scan time, sequences used, etc. Upload device session records through the EDC study site portal
1-Month Post MRI Scan Visit	30 days after MRI scan (0/+14 days)	
 Interrogate device Obtain in-clinic lead measurements: bipolar capture, sense, pacing and HVLI impedances^{1,2}

Study Visit	Visit Window	Study Procedures and Data Collection
		
 Evaluate subject for any adverse events and submit an AE CRF (as applicable). Report deviations, withdrawal and out of service as applicable Upload device session records through the EDC study site portal
System Revision (if applicable)	Can occur any time after implant	
 Interrogate device Obtain applicable in-clinic lead measurements: bipolar capture¹, sense², and pacing and HVLI impedances for cases where the lead was repositioned, or was replaced with another Durata/Optisure or Tendril/Isoflex, Quartet lead, or where the ICD/ CRT-D was replaced with another Ellipse ICD/ Quadra Assura MP CRT-D. Evaluate subject for any adverse events and submit an AE CRF (as applicable). Report deviations, withdrawal and out of service as applicable Upload device session records through the EDC study site portal

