8.4.7.2. Revisions after the MRI scan

If a system revision occurs after the MRI scan, then the subject will remain in the study until the subject completes the 1 Month Post Scan visit.

Any explanted devices or leads (including damaged leads, lead segments and lead fragments) should be returned to Abbott promptly for analysis. Document any change to the status of the lead and device (e.g. capped, removed) on the Product Out of Service CRF. Refer to

Table 9: System Revisions Scenarios After MRI Scan below to determine what actions need to be performed.

TABLE 8: SYSTEM REVISIONS SCENARIOS PRIOR TO MRI SCAN

System Revisions that occur prior to MRI Scan	Action	Data Submission

Revisions where the study ICD/ CRT-D system is still implanted:
 
 • Study lead(s) or the ICD/ CRT-D is repositioned or replaced, AND • The study ICD/ CRT-D and study lead(s) are still implanted, AND • No other non-MRI compatible material has been implanted 	
Obtain (if possible):
 
 • In-clinic bipolar and unipolar* capture threshold at a pulse width of 0.5 ms. for the applicable lead(s). Either the manual decrement or automatic (in-clinic, programmer based) method may be used to obtain the capture threshold. • In-clinic bipolar sensing amplitude for the applicable lead(s). Either the incremental or the automatic (in-clinic, programmer based) method may be used to obtain the sensing threshold. • In clinic atrial and ventricular bipolar and unipolar* lead impedance for the applicable lead • Retain the subject in the study. If the MRI scan visit has not occurred yet, then wait at least 45 days from the successful revision before completing the MRI scan visit. If the MRI scan visit has occurred, then follow the subject through the 1 Month Post Scan visit. 
*NOTE: Unipolar and bipolar configurations should be collected for LV leads
	
Complete and submit the appropriate forms to Abbott. Refer to Table 4. It is recommended that the following device printouts and measurements be maintained at the site.
 
 • FastPath Summary • Test Results with Freezes, Include Battery & Leads • Wrap-up Overview with full parameters

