
Revisions where the study ICD/ CRT-D system is still implanted
 
 The study ICD/ CRT-D and study lead(s) are still implanted, BUT A non-MRI compatible material(s) or device(s) has been implanted 
OR
 
Revisions where the study ICD/ CRT-D system is still implanted
 
 Study ICD/ CRT-D and study lead(s) is repositioned or replaced, AND The study ICD/ CRT-D and study lead(s) are still implanted, AND No other non-MRI compatible material has been implanted 	
Obtain (if possible):
 
 In-clinic bipolar and unipolar* capture threshold at a pulse width of 0.5 ms. for the applicable lead(s). Either the manual decrement or automatic (in-clinic, programmer based) method may be used to obtain the capture threshold. In-clinic bipolar sensing amplitude for the applicable lead(s). Either the incremental or the automatic (in-clinic, programmer based) method may be used to obtain the sensing threshold. In clinic bipolar and unipolar* lead pacing impedance for the applicable lead(s) Continue to follow the patient until the subject completes the 1 Month Post scan visit. 
*NOTE: Unipolar and bipolar configurations should be collected for LV leads
	Once required testing has been performed, complete and submit the appropriate forms to Abbott. Refer to Table 4

Revisions where the study lead(s) is not retained
 
 Study lead(s) is replaced with another lead, AND The study ICD/ CRT-D is still implanted, AND 	The subject will be withdrawn from the study.	
Document consenting information (name of the study, date of consent and inclusion/exclusion) in the subject's medical and/or study records.
 
Submit the Pre-MRI CRF, MRI CRF, System Revision CRF and Withdrawal CRF. Submit

System Revisions that occur after the MRI Scan	Action	Data Submission

 • A non-MRI compatible material(s) or device(s) has been implanted 		
Deviation, Product Out of Service, Adverse Event CRFs if applicable.
 
It is recommended that the following device printouts and measurements be maintained at the site.
 
 • FastPath Summary • Test Results with freezes, Include Battery & Leads • Wrap-up Overview with full parameters

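### SAP 3.5 item 2 limits the immediate post-scan lead measurements to subjects who also undergo 1-month testing, so valid same-day pre/post pairs are dropped for those who leave after the scan.

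*Combined protocol and SAP*

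**What the plan says.** SAP 3.5 item 2 deals in one sentence with "device electrical measurements at the MRI Scan Visit (pre- and post-scan) and at the 1-Month Post Scan Visit". It states that they "will be summarized based on Analysis Cohort subjects who undergo the 1-month post-MRI scan testing, and with evaluable device data available for analysis". One condition thus governs all three time points.

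On timing, Table 4 in protocol 8.4.4 says: "The pre-MRI scan, MRI, and post MRI scan procedures should occur on the same day". The 1-month visit follows 30 days after the scan, with a window of +14 days.

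The primary effectiveness analysis has a similar restriction. Under protocol 8.2.2 it "will be conducted on all subjects with complete data from pre- to 1-month post-MRI scan".

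Post-scan revisions are covered in protocol 8.4.7.2. The general rule is that if a revision follows the scan, "then the subject will remain in the study until the subject completes the 1 Month Post Scan visit". Table 9 repeats this for systems still implanted, including repositioned or replaced study leads: "Continue to follow the patient until the subject completes the 1 Month Post scan visit". One row of Table 9 differs. Where a study lead is not retained, the generator stays in and material that is not MRI compatible has been implanted, it says: "The subject will be withdrawn from the study". Protocol 8.4.6 also withdraws a subject whose whole system is removed without a study replacement.

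SAP 3.2 handles early leavers differently: those who die or withdraw before 1 month stay in the adverse-event denominator, with their last known status counted.

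**The concern.** The post-scan test is the measurement closest to the exposure under study. Whether a subject is later tested at 1 month can depend on what the scan did to the leads: an explant, a withdrawal or a death may follow from lead damage. Limiting the acute summary to 1-month attenders therefore selects on a later event that may be related to the acute result. It also applies to the acute data the same kind of selection that already affects the primary effectiveness endpoints. The pre/post pairs of non-attenders, which would help to judge whether their absence matters, are left out.

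No endpoint in this study is tested against a hypothesis, so the descriptive tables are the evidence. An acute threshold rise or sensing fall in a subject later lost could go unreported in any planned table.

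**Working it through.** **1. The plan's own figure.** Protocol 8.1.12 gives a required minimum of 10 subjects per group and anticipated attrition of 5 per group. 10 + 5 = 15 per group, and 4 × 15 = 60 in total. This reproduces. Anticipated attrition is 5/15 = 33.3%. The plan does not say how much of it falls before the scan and how much after.

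**2. Who loses an existing pre/post pair.** Comparing SAP 3.5 item 2 with the protocol's follow-up rules:

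| Event after the scan | 1-month testing? | Acute pair kept? |
|---|---|---|
| Revision, study system still implanted (8.4.7.2, Table 9) | Follow-up continues to it | Yes, if evaluable |
| Study lead not retained, all conditions of that Table 9 row met | No, withdrawn | No |
| Complete explant, no study replacement (8.4.6) | No, withdrawn | No |
| Death, other withdrawal, loss to follow-up (14.6) | No | No |

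On withdrawal, protocol 14.6 asks sites to attempt a final device check. SAP 3.5 does not say that this counts as 1-month testing.

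**3. What else would show an acute change.** The visible adverse-event trigger for pacing threshold (protocol 8.4.4.6 and 8.4.4.7.1) is a rise from pre-scan to one month, not from pre-scan to post-scan. No trigger for a sensing fall is visible. An acute change that the investigator does not judge to be an adverse device effect, in a subject who then leaves, may therefore appear nowhere.

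**4. Size, for one group.** Assumptions: all 15 subjects are scanned and have a post-scan measurement; 10 attend at 1 month (the planned minimum); attenders have no acute failure; any acute failure is among the 5 non-attenders. Subjects are counted, not leads. Intervals are exact two-sided 95% Clopper-Pearson, the method named in SAP 2.2.2. For 0 events in n the upper limit is 1 − 0.025^(1/n): for n = 10 it is 1 − 0.025^(0.1) = 30.8%, and for n = 15 it is 21.8%.

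| Acute failures among the 5 | Attenders only (SAP rule) | All scanned |
|---|---|---|
| 0 | 0/10 (0 to 30.8%) | 0/15 = 0% (0 to 21.8%) |
| 1 | 0/10 (0 to 30.8%) | 1/15 = 6.7% (0.2 to 31.9%) |
| 2 | 0/10 (0 to 30.8%) | 2/15 = 13.3% (1.7 to 40.5%) |
| 5 | 0/10 (0 to 30.8%) | 5/15 = 33.3% (11.8 to 61.6%) |

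The middle column is the same in every row, so the restricted data cannot distinguish these cases.

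**5. Smaller losses.** If 14 of 15 attend and the one non-attender failed acutely, the comparison is 0/14 (0 to 23.2%) against 1/15 = 6.7%. If all 5 losses come before the scan, no acute pair exists for them and the restriction changes nothing.

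**The case against.** The strongest defence is that the gap is narrow and partly covered elsewhere.

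- **Revisions.** A reader might infer that any lead revised after an early failure drops out. The documents do not support this. Protocol 8.4.7.2 keeps revised subjects to 1 month as a general rule, and the withdrawal row of Table 9 requires several conditions together. This objection stands and limits the point to the events listed in the working.
- **Other data.** A reader might infer that the pre/post pairs are the only information on subjects missing at 1 month. They are not. SAP 2.9 and 3.3 summarise reasons for missing data and early termination, SAP 3.2 keeps early leavers in the adverse-event tables, and SAP 3.5 item 4 reports adjudicated cause of death. A serious adverse device effect that needs invasive intervention or leads to death, and is adjudicated as MRI-related, counts in the primary safety endpoint. Acute loss of capture leading to intervention would therefore largely be seen. Smaller acute changes in a subject later lost need not be.
- **Comparability.** Using the same subjects at all three time points is a recognised way to make the columns comparable. That supports showing a completers-only version, but not showing it alone.
- **Redaction.** The Analysis Cohort definition (SAP 2.1) and much of SAP 2.3.2 are blacked out. A reader might infer from the visible text that the endpoint limits are never applied to post-scan values; that cannot be established. The redaction does not rescue item 2, however, because the 1-month condition is stated openly on top of the cohort, whatever that cohort is.
- **Status.** The item is descriptive, with no success criterion. This limits the weight of the point but does not remove it.

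**Conclusion.** The point holds in limited form. SAP 3.5 item 2, in unredacted text, conditions the acute pre/post result on 1-month testing. It drops valid same-day pairs from subjects who after the scan die, withdraw, are lost, are explanted without a study replacement, or meet the narrow Table 9 withdrawal row.

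The effect ranges from none, if all anticipated attrition precedes the scan, to the omission of 5 of 15 acute pairs in a group. In the latter case 0/10 is compatible with a true count anywhere from 0/15 to 5/15. The split of attrition and the number of acute failures are assumptions; the documents give neither.

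A reader might go further and infer that a planned post-scan success percentage will be inflated by a stated amount. The documents do not support that: the visible plan tabulates no such proportion for post-scan data, so the figures here illustrate what the restricted data can and cannot show.

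**What to change.** Amend SAP 3.5 item 2 as follows:

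1. Summarise pre-scan and post-scan measurements for every scanned subject with an evaluable same-day pair, whether or not the subject is tested at 1 month.
2. Keep the 1-month condition for the 1-month column only. A completers-only version can be shown beside it for comparability across time points.
3. List the pre- and post-scan values of each lead that has no 1-month measurement.

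A proportion of leads within the existing endpoint limits from pre-scan to post-scan would be an optional addition; the correction does not depend on it.

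The cost is a change of SAP wording and one extra table or listing, from data already collected. The number of subjects will differ between time points and should be shown in each column. No study procedure changes.

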2.3. Descriptive Endpoint(s)

Descriptive endpoints are reported using only summary statistics and no hypothesis tests will be performed.

The following data will be collected:

1. Demographics: gender, age, ethnicity, race, cardiac disease history, arrhythmia history, indication for ICD/CRT-D implant, history of smoking, etc.
2. Device electrical measurements at the MRI Scan Visit (pre- and post-scan) and at the 1 Month Post Scan Visit

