14.6. Criteria and Procedures for Subject Withdrawal

Each enrolled subject shall remain in the clinical study until completion of the required follow-up period; however, a subject's participation in any clinical study is voluntary and the subject has the right to withdraw at any time without penalty or loss of benefit.

Conceivable reasons for discontinuation may include, but not be limited to, the following:

- Subject death
- Subject voluntary withdrawal
- Subject lost-to follow-up as described below
- Subject's follow-up is terminated according to Section **23.1**.

The Sponsor must be notified of the reason(s) for subject discontinuation. The site will provide this information to the Sponsor. Investigators must also report this to their respective IRB/EC as defined by their institution's procedure(s).

No additional follow-up will be required or data recorded from subjects once withdrawn from the clinical study, except for the status (deceased/alive).

However, if a subject withdraws from the study due to problems related to the safety or performance of the device under investigation, the investigator shall ask for the subject's permission to follow his/her status/condition outside of the clinical study.

In case of subject withdrawal, the site should make attempts to schedule the subject for a final clinical study visit. At this final follow-up visit, the subject will undergo the following assessments:

- Device assessment including:
 - Fast Path Summary
 - Test results with Freezes, include battery and leads
 - Wrap-up overview with full parameters
 - Device MRI summary report (if performed)

Lost-to-Follow-up

If the subject misses two consecutive scheduled follow-up time points and the attempts at contacting the subject detailed below are unsuccessful, then the subject is considered lost-to-follow-up. Site personnel shall make all reasonable efforts to locate and communicate with the subject (and document these efforts in the source documents), including the following, at each contact time point:

- A minimum of two telephone calls on different days over the specified follow-up windows to contact the subject should be recorded in the source documentation, including date, time and initials of site personnel trying to make contact.
- If these attempts are unsuccessful, a letter (certified if applicable) should be sent to the subject.

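### SAP 3.5 item 2 limits the same-day pre- and post-scan readings to subjects who later have 1-month testing, so measured scan-day values of early exits are left out of that table

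*Combined protocol and SAP*

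**What the plan says.** Protocol 2.3 lists as a descriptive endpoint "Device electrical measurements at the MRI Scan Visit (pre- and post-scan) and at the 1 Month Post Scan Visit". SAP 1.4.3 repeats it. Neither attaches a population.

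SAP 3.5 item 2 does. It takes the "device electrical measurements at the MRI Scan Visit (pre- and post-scan) and at the 1-Month Post Scan Visit" together and says they "will be summarized based on Analysis Cohort subjects who undergo the 1-month post-MRI scan testing, and with evaluable device data available for analysis". The 1-month condition is written on top of membership of the Analysis Cohort, whose definition in SAP 2.1 is redacted.

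On timing, protocol Table 4 states: "The pre-MRI scan, MRI, and post MRI scan procedures should occur on the same day". The 1-month visit follows at 30 (+14) days.

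Subjects can leave in between:
- Protocol 14.6 names death, voluntary withdrawal and loss to follow-up.
- Protocol 8.4.6 withdraws a subject whose entire study system is removed with no study replacement to follow.
- The second row of protocol Table 9 says "The subject will be withdrawn from the study" when a study lead is replaced with another lead, the generator stays in, and non-MRI-compatible material or a device has been implanted. All three conditions must hold.

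After withdrawal, protocol 14.6 requires only vital status, although the site should try to arrange a final device check.

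**The concern.** The pre-scan and post-scan readings do not depend on the 1-month visit, yet the rule admits them only if that visit's testing takes place. That selects on something that happens after exposure and that the exposure could influence. Protocol Table 10 names lead heating with loss of sensing or capture, lead dislodgment and device damage as potential MRI-related events, and any of these could plausibly contribute to an early exit.

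The scan-day comparison is where an immediate effect on capture, sensing or impedance would show. If subjects with such a change leave early more often than others, the table understates it. If they leave at the same rate as others, the table is not biased, but it still discards observed values in groups planned at 10 to 15 subjects.

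The study has no hypothesis test and no success criterion (SAP 2.2 and 2.7), so what it delivers is its descriptive tables. Whether those tables include every measured subject therefore matters more than it would beside a formal test.

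**Working it through.** **Does another readable analysis show the scan-day values of early exits?**
- Both primary effectiveness endpoints (SAP 1.4.2) compare pre-scan with 1 month and do not use the post-scan reading. Protocol 8.2.2 adds: "The analysis of the effectiveness parameters will be conducted on all subjects with complete data from pre- to 1-month post-MRI scan".
- SAP 2.9 summarises reasons for missing primary endpoint data. It does not tabulate the scan-day readings.
- SAP 2.8 and 2.13 plan no subgroup or exploratory analysis.
- SAP 3.2 keeps subjects who die or withdraw in the adverse-event denominator, but it counts events, not measurements.
- The explicit rule for reporting a pacing-threshold rise (protocol 8.4.4.6 and 8.4.4.7.1) runs from pre-scan to 1 month. It need not capture a scan-day rise in someone who leaves before the second reading.

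No readable text restores the values. Within SAP 3.5, item 5 summarises key electrical measurements for non-study scans without any 1-month condition, and item 6 uses whatever the MRI Scan form holds.

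**The plan's own figure.** Protocol 8.1.12 requires 10 subjects per group and anticipates 5 lost: 10 + 5 = 15 per group, and 4 × 15 = 60 in total. This reproduces.

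**Share of measured pairs omitted.** Let k of the 5 anticipated losses per group fall after the scan. The documents do not give k, so the full range is shown. Measured pairs per group = 10 + k, pairs in the table = 10, share omitted = k/(10 + k).

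| k | Pairs measured per group | Pairs measured, 4 groups | Share omitted |
|---|---|---|---|
| 0 | 10 | 40 | 0% |
| 1 | 11 | 44 | 1/11 = 9.1% |
| 2 | 12 | 48 | 2/12 = 16.7% |
| 3 | 13 | 52 | 3/13 = 23.1% |
| 4 | 14 | 56 | 4/14 = 28.6% |
| 5 | 15 | 60 | 5/15 = 33.3% |

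**One case in one group.** Take k = 1 and suppose the subject who leaves is the only one with an acute change. The written rule shows 0/10 (0%, exact 95% interval 0 to 30.8%). Using all scanned subjects shows 1/11 (9.1%, 0.2 to 41.3%). The intervals are Clopper-Pearson, the method named in SAP 2.2.2.

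**Direction of the bias, on assumed rates.** Let p be the true share with an acute change, q1 the post-scan loss among them and q0 the loss among the rest. The share shown is p(1−q1) / [p(1−q1) + (1−p)(1−q0)]. None of these rates is in the documents. With p = 10% and q0 = 5%:
- q1 = 5%: 0.095/(0.095 + 0.855) = 10.0%, no bias
- q1 = 25%: 0.075/(0.075 + 0.855) = 8.1%
- q1 = 50%: 0.050/(0.050 + 0.855) = 5.5%
- q1 = 75%: 0.025/(0.025 + 0.855) = 2.8%

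**The case against.** **The safety pathway covers serious changes.** A reader might infer that an acute lead change in an early exit disappears from the study. The documents do not support that. Adverse device effects after MRI settings are programmed are reportable within 24 hours (protocol 16.1.2) and are adjudicated by the independent committee (protocol 8.3.2). They are summarised with early exits in the denominator (SAP 3.2). Deaths and termination reasons are also reported. This stands. What is left uncovered is a change that nobody reports as an adverse device effect.

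**Most revised subjects stay.** A reader might also infer that replacing a lead after the scan removes the subject. It does not. Protocol 8.4.7.2 keeps revised subjects to the 1-month visit, and the first row of Table 9 covers repositioned or replaced study components. The second row needs all three of its conditions, and protocol 8.4.6 needs removal of the whole system without a study replacement. Subjects who cannot tolerate the scan are not withdrawn (protocol 8.4.4.5). This stands too: the rule can remove affected subjects, but nothing shows that it removes those most likely to be affected.

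**Few may be lost.** The anticipated 5 losses per group run from consent. They therefore include failed implants, the 45-day wait and pre-scan screening failures. Only about a month remains after the scan, so k may be small or zero.

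**A fixed cohort is legitimate.** Using the same subjects at all three time points keeps paired summaries comparable. That is a reason to keep such a table, not to make it the only one.

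**Redaction.** SAP 2.1 and much of 2.3 cannot be read, so a further summary of post-scan values cannot be excluded. However, no definition of the Analysis Cohort would cancel a condition added to it in 3.5.

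**Conclusion.** The point holds as one about the completeness of a single descriptive table. As written, SAP 3.5 item 2 leaves out scan-day readings already taken from any scanned subject without 1-month testing, and no readable text brings them back. This can bias the scan-day table toward no acute change, but only if post-scan loss is related to such a change.

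The omitted share lies between 0% and 33.3% of measured pairs if exactly 10 per group are tested at 1 month and 5 are lost. The upper bound needs every loss to fall after the scan, which is unlikely given the pre-scan reasons for attrition, and the effect may be nil. The 8.1%, 5.5% and 2.8% figures show direction only, because their inputs are assumed.

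No error rate, power or success criterion changes. Importance is low to moderate, and the change is worth making because it is cheap.

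**What to change.** Replace the population in SAP 3.5 item 2 with wording such as:

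> Pre-scan and post-scan measurements and their change will be summarized for all subjects who began the study MRI scan and have the respective readings, whether or not 1-month testing was done. 1-month measurements and change to 1 month will be summarized for subjects with 1-month testing. n will be shown at each time point, and scan-day values of scanned subjects without a 1-month test will be listed.

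Tie the population to having begun the scan rather than to the Analysis Cohort. The cohort's definition is redacted, and if it already required 1-month data the new sentence would recover nobody. SAP 3.0 allows a population other than the Analysis Cohort where one is specified. Keep the completers-only table for the paired comparison across the three time points.

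The cost is a short change of SAP wording and one extra table or listing from data the MRI visit already collects. No new visits or subjects are needed. The downside is that n can differ between time points, which showing n at each one handles.
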